7.6 Epitope prediction algorithm

We have developed and optimized an epitope prediction algorithm for the identification and prioritization of neoantigens. This optimized epitope prediction algorithm is described below and in the Gubin 2014 manuscript [19]. We have established this algorithm in collaboration with [name], an internationally-known expert in tumor immunology [20, 80-87]. [name] was one of the first to use next generation sequencing technologies to identify neoantigens, demonstrating that these antigens are important tumor rejection antigens [20]. [name] and [name] have now optimized the epitope prediction algorithm and have demonstrated that cancer vaccines targeting neoantigens are associated with antitumor immunity [19].

The goal of the optimized epitope prediction algorithm is to identify and prioritize up to 20 neoantigens. The algorithm uses a combination of binding algorithms, processing algorithms and *in vitro* binding assays.

Mutations that are expressed in the breast cancer will be identified using the sequencing pipeline outlined in the document titled "Sequencing Pipeline." The predicted amino acid sequences corresponding to the expressed mutations will be pipelined through three class I MHC epitope-binding algorithms provided by the Immune Epitope Database and Analysis Resource (<http://www.immuneepitope.org>): (i) Stabilized Matrix Method (SMM) [90], (ii) Artificial Neural Network (ANN) [91], and (iii) NetMHCpan [92].

A prioritized list of binding epitopes (i.e. $IC_{50} < 500$ nM) will be generated after calculating the median binding affinity value for each mutant sequence (affinity value expressed as $1/IC_{50} \times 100$).

Filters will be applied to the list to (a) eliminate epitopes that are not processed efficiently by the immunoproteasome based on the NetChop algorithm [93] (peptides with a NetChop score ≥ 0.6 will be prioritized), (b) deprioritize epitopes from hypothetical proteins or that form a weaker predicted binding epitope than that expressed by the corresponding wild type sequence, (c) prioritize mutant epitopes that have the highest difference in predicted binding affinity compared to their wild type counterpart, and (d) incorporate expression profiles of wild type genes that correspond to the mutant antigen candidates in normal vs tumor cells.

To confirm the ability of prioritized neoantigens to bind to the corresponding MHC class I allele, we will synthesize peptides corresponding to the prioritized list of candidate epitopes. Synthetic peptides (> 95% purity) will be tested for binding to the respective class I MHC molecule using the T2 cell line, or one of its derivatives expressing common class I MHC alleles. The T2 cell line is deficient in transporters for antigen presentation (TAP), and as such is commonly used to assess binding of exogenously added peptides [94, 95]. Expression of class I MHC alleles is measured by staining of T2 cells with antibody specific for the class I MHC allele followed by flow cytometric analysis to measure the fluorescence intensity of the class I MHC allele on the cell surface. Data are typically expressed as Mean Fluorescence Intensity (MFI) by subtracting the baseline fluorescence intensity of the class I MHC allele to that measured after addition of exogenous peptide. Neoantigens that do not bind to the corresponding class I MHC allele will be deprioritized.

8 TREATMENT PLAN

8.1 Neoantigen DNA vaccine administration

The first neoantigen DNA vaccine injection will take place following completion of SOC therapy. The day of the first vaccine injection will be referred to as Day 1.

All subjects will be treated as outpatients in the Siteman Cancer Center.

The schedule of vaccination is Day 1, Day 29 \pm 7, Day 57 \pm 7, Day 85 \pm 7, Day 113 \pm 7, and Day 141 \pm 7 with at least 21 days between injection days. All study injections will be given intramuscularly using an integrated electroporation device (TDS-IM system, Ichor Medical Systems). At each vaccination time point, patients will receive two injections of the neoantigen DNA vaccine, one injection into each deltoid or lateralis. If both injections cannot be given on the same day, the patient will be asked to return to complete the second injection. Standard aseptic technique and precautions will be utilized in site preparation, vaccine administration, and medical waste disposal to ensure maximal safety of subjects and study personnel. Participants' vital signs will be monitored for 30 minutes post vaccine for safety purposes.

The propagation of electroporation inducing electrical fields in the muscle will result in brief, localized muscle contractions at the site of administration, which are transiently painful. The neoantigen DNA vaccines will be administered by an experienced nurse who has completed a training seminar on the use of the TDS-IM device.

The sites of immunization may be rotated for each of the immunizations. No injection will be given at a location in which the draining lymph nodes have been removed.

At the discretion of the treating physician, patients may be pre-medicated with lorazepam 1mg PO (or similar) at least 30 minutes but no greater than 60 minutes prior to the first injection. Patients may also receive a second dose of lorazepam (1 mg PO) (or similar) 10 minutes prior to injection. Patients may also receive pain medication at treating physicians' discretion PO at least 30 minutes but no greater than 60 minutes prior to the first injection.

At intervals throughout the study (both before and after vaccination) subjects will have blood drawn for immunologic assays. Any cells, serum or plasma not used will be stored for future immunological assays.

Please see **Section 10 Study Calendar** for details on study visit procedures and monitoring.

8.2 Durvalumab administration

For patients who are randomized to the neoantigen DNA vaccine plus durvalumab arm, the neoantigen-specific T cell response will be assessed prior to Day 85. If a neoantigen-specific T cell response is present, durvalumab will be started on Day 85, and will be administered Q4W (\pm 7 days) at a dose of 1500 mg over the course of 60 minutes. If a neoantigen-specific T cell response is not present, these patients will be replaced but may continue to receive the neoantigen DNA vaccine on study. They will not be transferred to the vaccine-only arm.

On days when subjects receive both vaccine injections and durvalumab infusions, they will receive the vaccine first, followed by observation for 30 minutes, followed by administration of durvalumab. Subjects will be monitored before, during and after the infusion with assessment of vital signs at the times specified in the Schedule of Assessment. Subjects are monitored (pulse rate, blood pressure) every 30 minutes during the infusion period (including times where infusion rate is slowed or temporarily stopped). Every effort should be made to give durvalumab and vaccine on the same day.

If weight falls to 30 kg or less, durvalumab will no longer be administered.

8.3 Replacement of patients

Patients who initially meet eligibility criteria and have a vaccine manufactured but either fail eligibility re-check based on durvalumab-specific criteria (but are still able to receive neoantigen vaccine safely) or are randomized to receive durvalumab but do not experience a neoantigen-specific T cell response (and thus

cannot receive durvalumab) may receive the neoantigen DNA vaccine but will be considered inevaluable and will be replaced. Safety and response data will be collected and analyzed separately.

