4.6 Randomization

Twenty-four patients will be enrolled. Patients will be randomized for participation in a 1:1 ratio to receive either neoantigen DNA vaccine alone or neoantigen DNA vaccine plus durvalumab. The randomization table will be generated using the SAS program PROC PLAN. Randomization will take place after the manufacture of the vaccine and after eligibility has been reconfirmed.

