15.2.1 Sample Size Calculations for Immunogenicity

A power analysis was performed using the paired t-test for over time differences (i.e., measures at Baseline vs. Day 1, Day 57) to test the first hypotheses that neoantigen DNA vaccines can induce and/or enhance neoantigen-specific T cell responses (e.g., the frequency of neoantigen-specific CD8 T cells in ELISPOT and multi-parameter flow cytometry). Assuming a moderate correlation between measures taken from the same individual, the designed sample size (n=24 patients) allows us 80% power at 1-sided 0.05 alpha level to detect a minimum of $0.5 \times SD$ for overtime changes. A power analysis was also performed using the 2-sample t-test for between-arm differences (i.e., measures at Day 113, Day 169) to test the second hypotheses that durvalumab will enhance the response to neoantigen DNA vaccines. We expect that the majority of the patients enrolled will remain in the study and lead to at least 10 evaluable patients/arm for such comparison. The designed sample size (n=10 patients/arm) provides us 80% power at 1-sided 0.05 alpha level to detect a minimum of $1.2 \times SD$ for between-group differences. Preliminary data from our phase 1 trial for mammaglobin-A DNA vaccine, though on patients with stable metastatic breast cancer and targeting a tissue-specific antigen, showed that the frequency of antigen-specific CD8 T cells can be measured with ~20% coefficient of variation ($CV=SD/Mean$). Therefore, the designed sample size allows us to detect ~10% for over-time differences and ~15% for between-group differences respectively. As a study to estimate preliminary information, we expect that ~20% difference will provide an adequate signal for immunogenicity. In addition, we anticipate that more power could be achieved because the actual data analysis will be performed using mixed model which uses data more efficiently and allows us to borrow information across multiple time points.

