15.3.2 Immune response

Neoantigen-specific T cell response to neoantigen DNA vaccines + durvalumab is the secondary objective of the trial. Neoantigen specific T cell responses will be measured by Luminex, ELISPOT, multiparametric flow cytometry, and CyTOF. The frequency of antigen-specific CD8 T cells in each arm at each time will be summarized using means, standard deviations and medians. The change over time as well as the difference between arms will also be compared using linear mixed model for repeated measurement data. The immunogenicity of the neoantigen DNA vaccine will also be analyzed qualitatively by summarizing the phenotypic and functional characteristics of epitope-specific CD8 T cells. Responses will be considered positive if the number of T cells after vaccination is greater than two standard deviations above the mean before vaccination [101]. The frequency of positive responses at each time point will be assessed and binomial response rates with 95% confidence interval estimates will be presented. In addition to presenting the binomial response rates, graphical and tabular summaries of the underlying distributions will be made.

To determine whether the observed difference is larger than might be expected by chance, a permutation test will be used to compare the observed test statistic to the distribution of test statistics that would be seen if there were no difference between the two arms. Specifically, we will randomly shuffle the data and calculate the test statistic from the shuffled data. This procedure will be repeated 10,000 times and the resultant testing statistics will provide an accurate representation of the null distribution. The observed test statistics of between-arm differences will be compared to the null distributions. For each outcome, the permuted p-value will be the fraction of permuted samples that resulted in a small statistic than the original sample [103].

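### Early T-cell non-responders are removed and replaced only in the durvalumab arm, so the Day 113/169 between-arm comparison of T-cell levels and response rates favours durvalumab even if it does nothing

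*Combined protocol and SAP*

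**What the plan says.** Section 4.6 allocates patients 1:1 and fixes the timing: "Randomization will take place after the manufacture of the vaccine and after eligibility has been reconfirmed". The study calendar (Section 10) places this at the eligibility re-check, ahead of Day 1. The vaccine schedule is the same in both arms, and durvalumab starts no earlier than Day 85.

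Section 8.2 has the T-cell response assessed before Day 85 in patients randomised to durvalumab. For that arm it says: "If a neoantigen-specific T cell response is not present, these patients will be replaced". They may carry on with vaccine but are not moved to the vaccine-only arm. Section 8.3 says that such a patient "may receive the neoantigen DNA vaccine but will be considered inevaluable and will be replaced", and adds: "Safety and response data will be collected and analyzed separately".

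Section 15.2.1 powers the second hypothesis, that durvalumab enhances the response, as a two-sample t-test at Day 113 and Day 169. It expects that enrolment will "lead to at least 10 evaluable patients/arm for such comparison". Section 15.3.2 gives the analysis: "The change over time as well as the difference between arms will also be compared using linear mixed model". It also reports positive-response rates at each time point, and for the arms "a permutation test will be used to compare the observed test statistic" with its shuffled distribution.

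Section 15 contains no early-response rule for the vaccine-alone arm, no as-randomised analysis set and no adjustment for the early response.

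**The concern.** This is an exclusion after randomisation, in one arm, on an early value of the outcome. The evaluable durvalumab arm consists only of patients already known to respond to the vaccine. The evaluable control arm is everyone. The arms then differ before durvalumab has had any chance to act.

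The test of hypothesis 2 could be positive with no durvalumab effect, and a positive result could not be separated from selection. The permutation test does not repair this: it assumes that the evaluable patients are exchangeable between arms, and the one-arm gate breaks that assumption.

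There is a second consequence for hypothesis 1. If the 24 patients in the paired Day 57 calculation are the evaluable ones, half of that set has been chosen for having responded by then, so the over-time change is overstated.

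The other group in the same sentence of Section 8.3, those failing the durvalumab-specific eligibility re-check, leaves before randomisation and does not cause this bias.

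**Working it through.** **The plan's own figure.** Inputs from Section 15.2.1: 10 per arm, one-sided 0.05, 1.2 SD, two-sample t-test. The noncentrality is 1.2/√(2/10) = 2.68 on 18 degrees of freedom, which gives 82.5% power. The smallest difference with 80% power is 1.16 SD, which rounds to 1.2. The figure reproduces, provided the two arms are comparable.

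**Assumed inputs.** Two quantities are needed that the documents do not give:
- p, the share of patients with a response at the Day 57 gate, taken from 0.9 down to 0.5;
- r, the correlation between the Day 57 and the Day 113/169 level, taken as 0.3, 0.5 and 0.7. The only guide is in Section 15.2.1, about the over-time comparison: "Assuming a moderate correlation between measures taken from the same individual".

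**Bias in levels.** Take a standard bivariate normal early and late level, with the gate removing the lowest 1 − p on the early one. With z = Φ⁻¹(1 − p), the late mean in the gated arm is shifted by r·φ(z)/p. For p = 0.7: z = −0.524, φ(z) = 0.348, φ(z)/p = 0.497, so at r = 0.5 the shift is 0.5 × 0.497 = 0.25 SD. At r = 0.5 the shift runs from 0.10 SD (p = 0.9) to 0.40 SD (p = 0.5).

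**False-positive rate.** Simulated trials with no durvalumab effect, 10 per arm, one-sided 0.05 pooled t-test at one time point:

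| r | p = 0.9 | 0.8 | 0.7 | 0.6 | 0.5 |
|---|---|---|---|---|---|
| 0.3 | 6.5% | 8% | 9% | 11% | 13% |
| 0.5 | 7.5% | 10% | 14% | 18% | 23% |
| 0.7 | 9% | 13.5% | 20% | 27% | 37% |

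A permutation test of the mean difference does the same: 11% (p = 0.8, r = 0.5), 14% (p = 0.7, r = 0.5), 22% (p = 0.5, r = 0.5) and 37% (p = 0.5, r = 0.7). With the same responder rule in both arms, the t-test returns to about 5% in every cell.

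**Response rates.** Let q = 1 − p and use the same cut-off c at both times. The late response rate among early responders is [1 − 2q + Φ₂(c, c; r)]/p. For q = 0.3 and r = 0.5 this is 0.795. The durvalumab arm would show about 80% against 70% in controls with no drug effect.

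**Change from Day 57.** If the mixed-model contrast is change from Day 57, the bias is (r − 1)·φ(z)/p. At p = 0.7 and r = 0.5 it is −0.25 SD, against durvalumab. Over p at r = 0.5 it runs from −0.10 to −0.40 SD, and false durvalumab wins fall to between about 0.5% and 3%. Section 15.3.2 does not name the contrast, so the direction of the bias depends on a choice still to be made.

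**The case against.** The strongest reply is one of weight. This is a phase 1 trial, safety is primary and descriptive, Section 15.2.1 calls the aim preliminary information, and the excluded patients' data are still collected and reported. That limits the reach of the problem but does not remove it: hypothesis 2 is one of two stated hypotheses and has its own power calculation. Reporting the excluded patients separately is open, but it confirms that they are outside the main comparison.

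On size, three points stand. The figures come from a single-time-point test, not the mixed model. Values of p and r are assumed, so 37% is a corner of the grid, and at p = 0.9 with r = 0.5 the error is only 7.5%. The 80% against 70% example assumes equal response rates early and late; if 90% responded later, the gap at p = 0.7, r = 0.5 would be 95% against 90%. Section 15.3.2 also names no explicit between-arm test of response rates, although any reading of those rates by arm carries the bias.

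On the remedy, adjusting for the Day 57 value also brings the error back to about 5% in this normal model without dropping controls. It relies on a linear relation carried into a range where the evaluable durvalumab arm has no patients, so it suits a supporting analysis. The plan also does not say how replacements are allocated, which an as-randomised analysis needs to know.

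**Conclusion.** The concern holds. As written, the plan compares selected responders with unselected controls, and the comparison of levels and response rates at Day 113/169 favours durvalumab. The direction is certain for levels if at least some durvalumab-arm patients fail the gate and early and later levels correlate positively. The bias vanishes if nobody fails the gate. The size is not known from the documents: over the assumed range the nominal 5% error becomes 6.5% to 37%, with about 14% at p = 0.7 and r = 0.5. This should be corrected before the hypothesis 2 analysis is run. It does not affect the primary safety objective, beyond the replaced patients being tabulated apart.

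**What to change.** Leave the dosing gate unchanged and amend Sections 8.3, 15.2.1 and 15.3.2:

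1. Apply one Day 57 response definition to both arms. Test hypothesis 2 in Day 57 responders of both arms, and report all patients as randomised alongside. State how replacements are allocated.
2. Estimate Day 57 response and change over time in all vaccinated patients, including those replaced.
3. Include every vaccinated patient in the safety tables by treatment received.
4. Name the between-arm contrast of the mixed model: level at Day 113/169, or change and from which baseline.
5. As a precaution, take the Day 57 results used for analysis from the same assay runs in both arms. Section 11.3 batches samples at completion unless otherwise noted, whereas the gate needs a durvalumab-arm result before Day 85.
6. Restate the power.

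The cost is mostly wording, plus classifying vaccine-alone patients from Day 57 blood that Section 11.3.1 already schedules. The real price is fewer controls. Power for 1.2 SD is 82.5% at 10 v 10 and 81% at 12 v 8, but 75%, 71% and 67% at 10 v 7, 6 and 5. The difference detectable with 80% power rises from 1.16 SD to 1.28, 1.35 and 1.44 SD. The loss is smaller if responders vary less: at p = 0.7 and r = 0.5 their SD is 0.934 of the full SD, and 10 v 7 gives 80% for 1.2 full-population SD. Keeping 10 responders per arm needs 20/p randomised: 25, 29 or 34 at p = 0.8, 0.7 or 0.6, against 24 planned.

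The as-randomised analysis has less power. With 12 per arm, r = 0.5 and a 1.2 SD effect only in early responders, it is about 64%, 53% and 42% at 20%, 30% and 40% non-response.

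Randomising after the Day 57 result would also remove the bias, but that is a design amendment to Section 4.6 and the calendar.

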- Study Plan:** Twenty-four breast cancer patients will be enrolled. Tumor tissue and peripheral blood will be obtained prior to initiation of any treatment for sequencing and correlative studies. These analyses will inform the design of the neoantigen DNA vaccines.
- The neoantigen DNA vaccines will be manufactured at Siteman Cancer Center and then administered following standard of care therapy. It is anticipated that standard of care therapy in this clinical context will include surgery, adjuvant or neoadjuvant chemotherapy (AC + T or similar regimen), and adjuvant radiation therapy, taking a total of approximately 6 months to complete.
- Following standard of care adjuvant therapy, patients will be randomized to receive either a neoantigen DNA vaccine alone, or a neoantigen DNA vaccine + durvalumab. The vaccine will be administered by intramuscular injection on Day 1, Day 29 \pm 7, Day 57 \pm 7, Day 85 \pm 7, Day 113 \pm 7, and Day 141 \pm 7 with at

least 21 days between injection days. Each DNA vaccination will be 4 mg vaccine administered intramuscularly using a TriGrid electroporation device.

[figure not shown]
For patients who are randomized to neoantigen DNA vaccine + durvalumab, the neoantigen-specific T cell response will be assessed after two vaccinations (Day 57). If a neoantigen-specific T cell response is present, durvalumab will be administered every 28 days at a dose of 1500 mg beginning on Day 85.

Study Duration: Each subject will be followed for at least 12 months following the date of last treatment. Additional follow-up visits or telephone contact will be scheduled annually thereafter if the patient is alive and available for follow-up.

Study Endpoints: The phenotype and function of class I and II neoantigen-specific T cell response will be assessed by ELISPOT, luminex, multiparametric flow cytometry, and CyTOF. Safety endpoints include safety of the neoantigen DNA vaccine alone, or neoantigen DNA vaccine plus durvalumab. Toxicity will be graded according to the National Cancer Institute Common Terminology Criteria for Adverse Events version 4.03.

SCHEMA

Anti-PD-L1 antibody (MEDI4736)
Adjuvant personalized breast cancer vaccine (SLP with poly IC:LC)

PROTOCOL SIGNATURE PAGE

A RANDOMIZED PHASE 1 TRIAL OF NEOANTIGEN DNA VACCINE ALONE VS. NEOANTIGEN VACCINE PLUS DURVALUMAB IN TRIPLE NEGATIVE BREAST CANCER PATIENTS FOLLOWING STANDARD OF CARE THERAPY

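### Replacing durvalumab-arm non-responders selects that arm on the hypothesis 1 outcome, so its pre-durvalumab response rate and any pooled estimate of vaccine immunogenicity are biased upward unless Section 15 adds those patients back

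*Combined protocol and SAP*

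**What the plan says.** The synopsis places the T cell check for the durvalumab arm after two vaccinations, at Day 57. Section 8.2 says "the neoantigen-specific T cell response will be assessed prior to Day 85", the visit at which durvalumab would start. So the check falls while every patient in both arms has had vaccine only.

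Section 8.3 covers durvalumab-arm patients who fail this check. They "may receive the neoantigen DNA vaccine but will be considered inevaluable and will be replaced. Safety and response data will be collected and analyzed separately". Section 8.2 adds: "They will not be transferred to the vaccine-only arm". No corresponding rule removes a vaccine-alone patient for lack of response. Section 8.3 applies the same handling to patients who fail the durvalumab-specific part of the eligibility re-check. Under Section 4.6, randomization comes only after eligibility is reconfirmed, so those patients belong to neither arm.

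Section 15.2.1 sizes a paired t-test, with Day 57 among its time points and n=24, "to test the first hypotheses that neoantigen DNA vaccines can induce and/or enhance neoantigen-specific T cell responses". Section 15.3.2 calls a response positive when it exceeds the pre-vaccination mean by more than two standard deviations, and says that "binomial response rates with 95% confidence interval estimates will be presented" for each time point. Neither section names the analysis population for hypothesis 1 or for the response rates, and neither says that replaced patients are added back.

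**The concern.** Hypothesis 1 asks whether the vaccine produces a T cell response. Up to Day 57 both arms receive identical treatment, so both inform that question. The only handling rule in the protocol takes non-responders out of one arm and fills their places until responders occupy them. Membership of the evaluable durvalumab arm then depends on the quantity being estimated.

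Two outputs are exposed. One is the durvalumab arm's response rate and interval at Day 57, which would describe the filter more than the vaccine. The other is any pooled summary or pooled test of change from baseline, which would show a rise even if the mean did not move. The between-arm comparison at Days 113 and 169 is a different analysis and is not the subject here.

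**Working it through.** **Inputs from the documents.** n=24, one-sided alpha 0.05, 80% power and a detectable change of 0.5 SD (15.2.1); 1:1 allocation, hence 12 per arm (4.6); replacement of durvalumab-arm non-responders (8.2, 8.3).

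**Assumptions.** The documents give no Day 57 response probability p, so I use 30, 50, 70 and 90%. Within-patient correlation is described only as moderate, so I use 0.5. Replacements are taken to go into the durvalumab arm until it holds 12 responders.

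**The plan's own figure.** The SD of a within-patient difference is SD × √(2(1−ρ)), which equals 1 SD at ρ = 0.5. With n=24 and a change of 0.5 SD, power is 0.789 by the normal approximation and 0.768 by the exact noncentral t. The stated 80% is reproduced to within about 3 points. For ρ from 0.3 to 0.7 the exact figure runs from 0.64 to 0.92.

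**Response rate.** If the gate and the analysed response were the same measurement, the evaluable durvalumab arm would show 12/12 = 100% (exact 95% CI 74 to 100) whatever p is. The vaccine-alone arm would show p on average. A pooled rate is (12 + 12p)/24 = (1 + p)/2, an overstatement of (1 − p)/2. Filling the arm takes 12/p randomized patients.

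| True p | Pooled evaluable rate | Overstatement | Randomized to durvalumab to get 12 responders |
|---|---|---|---|
| 30% | 65% | 35 points | 40 |
| 50% | 75% | 25 points | 24 |
| 70% | 85% | 15 points | about 17 |
| 90% | 95% | 5 points | about 13 |

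Example at p = 50%. The evaluable set gives (12 + 6)/24 = 18/24 = 75% (95% CI 53 to 90). All vaccinated patients give 18/(24 + 12) = 18/36 = 50% (33 to 67).

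**Test of change.** Take no true mean change, 12 unselected patients, and 12 patients who passed a gate that a fraction p pass. Let c be the correlation between the gate measure and the analysed change. The pooled mean shifts by c × φ(z)/(2p) SD, where z is the (1 − p) quantile of the standard normal. At p = 0.5 and c = 1 this is 0.399/(2 × 0.5) = 0.40 SD. The error of a one-sided 5% t-test with 23 df comes from 40,000 simulated trials per cell.

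| Gate pass rate | Shift, c = 1 | Error, c = 1 | Shift, c = 0.5 | Error, c = 0.5 |
|---|---|---|---|---|
| 30% | 0.58 SD | 90% | 0.29 SD | 39% |
| 50% | 0.40 SD | 67% | 0.20 SD | 25% |
| 70% | 0.25 SD | 37% | 0.12 SD | 15% |
| 90% | 0.10 SD | 12% | 0.05 SD | 8% |

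The case c = 1 means that gate and test use the same change score. The case c = 0.5 is what results when the gate is the Day 57 value and the test is the change from baseline with ρ = 0.5. A separate simulation of that gate (4,000 trials per cell) gave 38, 24, 14 and 7%. Keeping every vaccinated patient in the test returned the error to between 4.6 and 5.6%.

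**The case against.** The strongest reply is that exclusion from hypothesis 1 is nowhere stated. Section 15.2.1 sizes hypothesis 1 on 24 patients, which is the number enrolled, and speaks of evaluable patients only for the between-arm comparison. One could read *inevaluable* in 8.3 as referring to durvalumab alone. That reading is possible, so a reader should not infer that the plan expressly computes hypothesis 1 without the non-responders. But the only handling given is replacement and separate analysis, explicitly including response data, and nothing in Section 15 reverses it.

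A reader might also infer that the durvalumab arm's rate is 100% by construction. The documents do not support that. The gate's assay and threshold are not defined, the two-standard-deviation rule is not tied to it, four assays are listed, and Section 11.3 has specimens assayed together at the end unless otherwise noted. The analysed Day 57 value may therefore differ from the gate value. The rate is pushed toward 100%, not fixed there.

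Three further points stand. Section 15.3.2 summarises frequencies by arm and never says that response rates are pooled. The planned analysis is a linear mixed model, so the simulated errors belong to the paired test used for sizing. And the null scenario needs a gate looser than the two-standard-deviation rule: on one normal measure with no effect, about 2.3% would pass, and filling 12 places would take about 12/0.023 ≈ 520 patients. The error figures therefore illustrate looser gates. The response-rate distortion needs no null assumption.

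Finally, the non-responders' data are kept and can be added back. That makes the remedy cheap, but separate reporting does not correct the main figure.

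**Conclusion.** The point holds as a should-fix. Followed as written, 8.2 and 8.3 select one arm on the hypothesis 1 outcome while leaving the other unselected, and Section 15 does not undo this. The durvalumab arm's pre-durvalumab response rate is then biased upward, as is any pooled estimate or test of change. The vaccine-alone arm's rate is not, so it would be wrong to conclude that the trial has no unbiased estimate of the vaccine's response rate.

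The size depends on an unstated response probability: a pooled overstatement of 35 points at p = 30%, falling to 5 points at 90%. Inflation of the sizing test ranges from 8% to 90% against a nominal 5%, depending on the pass rate and on how closely the gate matches the analysed measure. These are illustrations, not the operating characteristics of the mixed model. Immunogenicity is a secondary objective in a trial whose primary objective is safety, which limits the severity.

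**What to change.** In Section 15.3.2, state that hypothesis 1 and all response rates from samples taken before the first durvalumab dose (through Day 57, and the Day 85 sample where drawn pre-dose) use every randomized, vaccinated patient with the relevant sample, including durvalumab-arm non-responders replaced under 8.3. In Section 8.3, limit *inevaluable* to questions that depend on durvalumab exposure. State also that patients who fail the durvalumab-specific eligibility re-check, and so are never randomized, are reported separately or in a vaccine-only sensitivity analysis.

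The cost is a few sentences. Section 8.3 already provides for collecting the data, and no treatment decision changes. The reported response rate becomes less favourable, and the denominator for hypothesis 1 may exceed 24.
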